## Protocol:

### Introduction

Patients' increasing desire for aesthetic restorations has led to the use of direct resin composites as the most versatile restoration for both anterior and posterior teeth, with evidence for their success. However, polymerization shrinkage and indeed the strains it generates are still one of the main reasons for resin composite restoration failures. This is because it applies tension to the tooth-restoration interface over time, endangering the bonding integrity. Furthermore, these stresses negatively affect cavity margins with leakage and subsequent carious lesion development.

These stresses are widely recognized to be affected by the placement techniques. The standard method for avoiding the clinical effects of polymerization stress is incremental layering. The drawbacks of this technique are the possibilities of voids or contaminants inclusion between layers, and difficulties in filling conservative cavities. In addition to, a need for restorative procedures that effectively shorten restoration time. In this regard, bulk-fill high-viscosity(regular), and low-viscosity (flowable) methacrylate-based resin composites had been evolved.

Different viscosities are due to filler content that has direct relation with material modulus of elasticity. Bulk-fill low-viscosity resin composites (BLRC) are indicated as liners and stress absorbers in class I and class II cavities, requiring an additional layer high-viscosity type. While high viscosity (BHRC) types can be inserted up to 5 mm increment, without the need of a veneering layer. The increased curing depth were attributed to monomers which act as modulators in the polymerization reaction, resulting in reduced shrinkage.

Scientific evidence has shown that bulk-fill resin composites have comparable polymerization shrinkage and stress, depth of cure, physic mechanical properties, and marginal adaptation when compared to conventional composites. Other studies have revealed greater values for shrinkage vectors and a higher tendency for debonding. In relation to their clinical performance, data investigating the high-viscosity methacrylate based types had a heterogeneous behaviour and depended mainly in their chemical composition. Most of the studies have reported similar results related to marginal degradation when compared to conventional resin composites.

Bulk-fill low-viscosity resin composites (BLRC) as liners demonstrated a stress reduction ability in posterior resin composite restorations, thereby exhibiting a high level of clinical efficacy over three years evaluation. Besides, their low elastic modulus may provide a certain stress-absorbing layer, thus relieving the polymerization stress of the veneering regular viscosity composites. Moreover, subsequent layer of higher modulus resin composites can be absorbed by an elastic intermediary layer, lowering stress at the tooth-restoration interface. In a RCT one of the restorative systems that used BLRC liner showed the lowest surface staining.

Despite, contradictory evidence had reported decreased adaption and higher polymerization shrinkage stress than the high-viscosity counterpart and other study found no improvement in the clinical performance of a class II restoration. It is unknown, nevertheless, whether low viscosity bulk-fill composites would be susceptible to proximal contact defects comparable to those reported in glass ionomer restoratives.

Resin matrix plays an important role on the shrinkage behaviour of resin composite restorations. The high molecular weight bis-GMA (bisphenol A-glycidyl methacrylate) has been the main monomer used in methacrylate-based resin composites since their development. Due to the high viscosity of this monomer, low molecular weight monomers (diluents) were added to the final blend to get a suitable formulation for clinical use and to allow filler inclusion. These diluent monomers were supposed to increase the polymerization shrinkage of resin composites.

To reduce the clinical problems associated with the conventional methacrylate based resin composites, Ormocers were developed. They claimed to lower polymerization stress due to their reduced amount of organic resin. On the other hand, their first launched generations did not make any clear progress over the methacrylate-based resin composites. A probable explanation of the attained findings was the inclusion of methacrylate monomers beside ormocer molecule that served as diluents. A pure ormocer resin composite was then introduced to the market and it was placed by incremental layering.

In addition to layering method, the pure material had been implemented for bulk-filling with two viscosities like methacrylates (high viscosity, low viscosity). In comparison with methacrylate resin composites, the pure ormocer material were supposed to lower polymerization shrinkage. Bulk-fill high-viscosity ormocer-based resin composites(BHORC) may be superior alternative to the standard layering method, given similar clinical performance after 24 months, with the advantage of simplified procedures. In addition, a RCT utilized the pure layered ormocer material (Admira-fusion) and found non-significant differences over the compared methacrylate based resin composites after 24 months in class II restorations.

As regard lining ormocer-based resin composites, the data is scarce. Torres et al reported in a one randomized clinical trial to have no influence in their clinical performance. So that the aim of this randomized, split-mouth clinical trial was to evaluate the clinical performance of class II restorations made with the use of BHORC versus BHMRC composites either placed alone or with the effect of BLRC liner of the same type after 2 years follow up.

The null hypotheses in the study were as follows: (1) Different types of matrix structures (ormocer vs. methacrylate) have no effect on the clinical performance of restorations; (2) A layer of bulk-fill resin composite liner of the same category would not affect clinical parameters evaluated.

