### **Aim of the study**

The current study was intended to evaluate the effect of flowable lining resin composites on 2-year clinical performance of bulk-fill ormocer versus methacrylate-based restorative systems in class II cavities according to FDI criteria.

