### **Null hypothesis**

The null hypothesis that will be tested in this project is that there would be no significant difference among the four tested restorative strategies at different clinical evaluation periods.

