## **Materials and Methods**

### **Materials**

Bulk-fill high viscosity methacrylate-based resin composite (BHMRC) (XTra-fill Voco, Germany), Bulk-fill high-viscosity ormocer-based resin composite (BHORC) (Admira-Fusion-Xtra Voco, Germany), Bulk-fill low-viscosity methacrylate-based resin composite (XTra-Base Voco, Germany) (BLMRC) and bulk-fill low-viscosity ormocer-based resin composite (BLORC) (Admira-Fusion-Base Voco, Germany). All restorations were performed using the universal adhesive (Futura U bond Voco, Germany).

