## **Randomization**

Randomization was applied by noting each tooth to be restored (FDI 2- digit code) on one paper and type of restorative strategy on a second. First, a tooth number was drawn blindly. Subsequently a restorative protocol was allocated to this tooth by blind drawing. This procedure was repeated if more than three restorations must be placed.

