## **Interventions: Restorative procedures**

A split-mouth design was used in this study. For ormocer- based resin composite restorative system, it will be placed without resin flowable liner in one side, while it will be lined in the other side. The same protocol will be applied for methacrylate-based resin composite restorative system. Hence, each patient will receive four restorations with different strategies. All restorative procedures will be carried out by a single operator.

After administration of local anesthetic, rubber dam will be placed. The cavity preparation was then carried out with an outline limited to caries progression. The cavities depth in mm will be measured by a periodontal probe to give an idea about the thickness of the flowable composite liner (when used) and preserve 2 mm depth for the overlying resin. Restorative systems were then be applied according to the instructions recommended by their manufactures. Sectional pre-contoured matrix with ring, and wave like contour plastic wedges was used to restore the shape of the proximal walls. Adhesive and resin composites was cured using a LED (light

emitting diode) curing unit in the standard application mode and an output of 650 mW/cm^2.

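### The separate matrix and liner hypotheses have no estimate, interval or test; the only comparison between strategies is a four-group chi-square

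*Combined protocol and SAP*

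**What the plan says.** The Introduction ends with two separate null hypotheses. One concerns the matrix: "Different types of matrix structures (ormocer vs. methacrylate) have no effect on the clinical performance of restorations". The other concerns the liner: "A layer of bulk-fill resin composite liner of the same category would not affect clinical parameters evaluated". The Aim of the study then puts the liner first: to "evaluate the effect of flowable lining resin composites on 2-year clinical performance" of ormocer and methacrylate systems.

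The section headed Null hypothesis states something different, a single global null that "there would be no significant difference among the four tested restorative strategies at different clinical evaluation periods".

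Under Interventions, each material is placed with a liner on one side of the mouth and without on the other, and "each patient will receive four restorations with different strategies". The design is therefore a 2 x 2 factorial (matrix by liner) within each of 30 patients. Under Materials, each matrix has its own liner product.

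The Statistical analysis section contains two tests. A chi-square compares the four groups at each follow-up. A marginal homogeneity test compares visits within one group. The results table gives counts and p-values only.

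**The concern.** The plan asks about two factors and analyses neither. The chi-square has 3 degrees of freedom and answers only whether the four strategies differ somewhere. Marginal homogeneity looks at change over time within one strategy and compares no strategies.

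Had the chi-square rejected, the result could not have been assigned to matrix, to liner or to their interaction. It did not reject, and a large p-value does not say how large a liner effect is still possible. That second question is what the aim turns on. The Introduction itself says it is unknown whether low-viscosity bulk-fill materials are prone to proximal contact defects. The table shows contact events at 24 months, but the plan attaches no liner estimate or interval to them. Because each patient carries all four combinations, both effects can be estimated within patient from data already collected.

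**Working it through.** **Inputs.** There are 30 restorations per strategy. An event is a score of 2 or worse, and counts are in the order XF, XB, AFX, AFB:
- interproximal contact at 24 months: 1, 2, 3, 2
- colour match at 24 months: 2, 1, 0, 0
- baseline sensitivity: 1, 0, 2, 0

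The table does not define its codes. From the product names I take XF and XB as methacrylate, AFX and AFB as ormocer, and XB and AFB as lined.

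**Reproducing the plan's figures.** A Pearson chi-square on each 2 x 4 table (3 df) gives 1.071, p=0.784 for contact, and 3.761, p=0.288 for both colour and baseline sensitivity. All three match the table.

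**Contrasts.** For each patient, take the mean event indicator at one level of a factor minus the mean at the other. Averaged over patients:
- liner (lined minus unlined) = [(XB+AFB) - (XF+AFX)]/60
- matrix (ormocer minus methacrylate) = [(AFX+AFB) - (XF+XB)]/60

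Point estimates:
- contact, liner: (4 - 4)/60 = 0.0 points
- contact, matrix: (5 - 3)/60 = +3.3
- contact, liner within methacrylate: (2 - 1)/30 = +3.3
- contact, liner within ormocer: (2 - 3)/30 = -3.3
- contact, interaction: -3.3 - 3.3 = -6.7 (unrounded, -2/30)
- colour, liner: (1 - 2)/60 = -1.7
- colour, matrix: (0 - 3)/60 = -5.0

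**Intervals.** The table gives margins only, not which events share a patient. I therefore enumerated every way of placing the tabulated events over 30 patients (85 for contact, 2 each for colour and sensitivity). For each I computed a score-type 95% interval for the mean within-patient difference (constrained multinomial maximum likelihood, Tango-type) and an exact sign-flip p-value.

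| Contrast | Estimate (points) | Narrowest 95% CI | Widest 95% CI | Sign-flip p |
|---|---|---|---|---|
| Contact, liner | 0.0 | -11.4 to +11.4 | -14.6 to +16.1 | 1.0 |
| Contact, matrix | +3.3 | -8.4 to +14.3 | -11.6 to +19.1 | 0.50 to 1.0 |
| Contact, interaction | -6.7 | -28.6 to +16.8 | -38.1 to +23.3 | 0.50 to 1.0 |
| Contact, liner in methacrylate | +3.3 | -8.4 to +16.7 | -11.3 to +18.8 | 1.0 |
| Contact, liner in ormocer | -3.3 | -16.7 to +8.4 | -20.7 to +13.7 | 1.0 |
| Colour, liner | -1.7 | -12.8 to +9.9 | same | 1.0 |
| Colour, matrix | -5.0 | -15.8 to +6.9 | -18.3 to +6.9 | 0.25 to 0.50 |

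Baseline sensitivity mirrors colour with the factors exchanged: liner -5.0 with the intervals and p-values of the colour matrix row, and matrix +1.7 (-9.9 to +12.8).

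**Criteria without events.** Six criteria have no score of 2 or worse at 24 months, or seven with tooth integrity, whose extracted row shows only four visits. With no discordant patient the score limit is z²/(n + z²) = 3.841/(30 + 3.841) = 0.1135, so the interval is -11.4 to +11.4 points. As a cross-check, the exact 97.5% upper limit for 0 of 30 patients is 1 - 0.025^(1/30) = 11.6%.

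**Power.** I simulated a single-factor effect with 30 patients, zero within-patient correlation, an assumed alpha of 0.05 and 20,000 runs.

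| Event rates | Chi-square | Sign-flip |
|---|---|---|
| 6.7% vs 3.3% | 6.0% | 4.0% |
| 5% vs 0% | 13.7% | 6.5% |
| 10% vs 5% | 8.9% | 8.3% |
| 10% vs 3.3% | 14.8% | 16.1% |

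The factor test offers no general gain in power at these rates, so the argument rests on estimation.

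**Why the omnibus test should stay.** A crossed pattern of 1, 7, 7, 1 events gives chi-square 10.385, p=0.016. Both main contrasts are then zero, since each compares 8/60 with 8/60.

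**The case against.** The strongest reply is that the section headed Null hypothesis names the global null as the one to be tested, and the chi-square tests exactly that. If the global null is true, neither factor has an effect. On this reading the defect is a disagreement between two sections, curable by wording. The mismatch is real, but it leaves the stated aim without an analysis, and failing to reject the global null sets no limit on a liner effect.

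Several further points stand as qualifications:
- The Aim is chiefly a liner question. Only the Introduction separates matrix from liner.
- Every between-group p-value is 0.288 or larger, so failed attribution is hypothetical here. Given the tabulated 24-month counts, the smallest sign-flip p either factor can reach is 0.25. Only the intervals add information.
- The colour counts are the same at baseline as at 24 months, so that difference was present at placement. Only contact had changed by 24 months.
- Interval width depends on method. Unpaired Newcombe intervals on 60 versus 60 give ±10.1 for contact liner, and ±6.0 where there are no events (3.841/63.841 = 0.060). They treat restorations in one mouth as independent, so I do not prefer them. The widest limits in the table are possible pairings, not observed ones.
- The Randomization section speaks of repeating the draw when more than three restorations are needed, which sits awkwardly with four per patient. The contrasts need one restoration of each strategy in each mouth. The eligibility criteria and the 30 per group support this, but it should be confirmed.
- Five quantities over nine criteria is 45 post hoc estimates, many of them identical.

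**Conclusion.** The concern holds, and the plan should be changed. Followed exactly, it gives no estimate, interval or test for the matrix hypothesis, the liner hypothesis or their interaction, although the liner effect is the aim. Nothing reported reverses and no power is gained at event rates of 10% or less. The loss is that p=0.784 and p=1.0 stand where the reader needs intervals reaching at least about 11 points either side of zero, and up to about 21 points for the liner effect within ormocer.

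The absence of a factor analysis is plain from the text and rests on no assumption. The illustrative figures assume the lined and unlined codes read from product names, one restoration per strategy in each of 30 patients, and the unknown within-patient pairing, which is shown as a range.

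**What to change.** 1. Reconcile the Introduction with the Null hypothesis section, and define the group codes. The table footnote names three groups (EXF, SDR, TNFBF) that are not columns of the table.
2. Add to the Statistical analysis section, for each FDI criterion at 24 months with the event defined as score 2 or worse, two within-patient contrasts: matrix (XF+XB against AFX+AFB) and liner (XF+AFX against XB+AFB). Report each as a paired risk difference with an exact or score-type 95% interval.
3. Test each contrast by an exact sign-flip of each patient's whole difference. If the draw is random, this is valid under the free draw in Randomization ("Subsequently a restorative protocol was allocated to this tooth by blind drawing") and under the side split in Interventions ("it will be placed without resin flowable liner in one side, while it will be lined in the other side").
4. Show alongside, with intervals, the interaction and the liner difference within each matrix. Each matrix has its own liner product, and opposite effects cancel in the pooled contrast, as they do for contact.
5. Keep the four-group comparison, which can detect crossed patterns.
6. Avoid an unpenalised logistic model. A zero count at one factor level makes the matrix estimate diverge for colour and the liner estimate diverge for baseline sensitivity.
7. Because the 24-month results are already tabulated, label the contrasts as specified after the data were seen. Make estimates and intervals the main output, and treat p-values, unadjusted over nine criteria, as descriptive.

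The cost is some rewording and a short analysis of existing patient-level data, since the table's margins do not show pairing. The contrasts cannot be presented as confirmatory, and with so few events the intervals will be wide.

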### **Aim of the study**

The current study was intended to evaluate the effect of flowable lining resin composites on 2-year clinical performance of bulk-fill ormocer versus methacrylate-based restorative systems in class II cavities according to FDI criteria.

### **Null hypothesis**

The null hypothesis that will be tested in this project is that there would be no significant difference among the four tested restorative strategies at different clinical evaluation periods.

## **Materials and Methods**

### **Materials**

Bulk-fill high viscosity methacrylate-based resin composite (BHMRC) (XTra-fill Voco, Germany), Bulk-fill high-viscosity ormocer-based resin composite (BHORC) (Admira-Fusion-Xtra Voco, Germany), Bulk-fill low-viscosity methacrylate-based resin composite (XTra-Base Voco, Germany) (BLMRC) and bulk-fill low-viscosity ormocer-based resin composite (BLORC) (Admira-Fusion-Base Voco, Germany). All restorations were performed using the universal adhesive (Futura U bond Voco, Germany).

### **Methods**

#### **Clinical trial design**

This clinical trial will be conducted according to CONSORT guidelines for Randomized Clinical Trials (RCTs). It will be carried out after gaining approval from Medical Ethics Committee of Mansoura University.

#### **Recruitment**

Patients enrolled in this study were from the Outpatient Clinic at Mansoura University, Faculty of Dentistry. Patients were informed on the background of the study and who accepted the study condition signed a consent form. The consent form was approved by the ethical committee at faculty of dentistry, Mansoura University.

#### **Eligibility criteria**

Participants were examined to form a group with 30 patients that justify the inclusion and exclusion criteria. Patients were required to have good general health, be older than 18 years old. Patients with extremely poor oral hygiene, severe or chronic periodontitis, or heavy bruxism habits will be excluded from the study.

Patients had to present at least four teeth with class II cavities to be restored (molars or premolar). Also, unsatisfactory class II restorations that are moderately deep with an adjacent tooth was involved.

## **Randomization**

Randomization was applied by noting each tooth to be restored (FDI 2- digit code) on one paper and type of restorative strategy on a second. First, a tooth number was drawn blindly. Subsequently a restorative protocol was allocated to this tooth by blind drawing. This procedure was repeated if more than three restorations must be placed.

## **Interventions: Restorative procedures**

A split-mouth design was used in this study. For ormocer- based resin composite restorative system, it will be placed without resin flowable liner in one side, while it will be lined in the other side. The same protocol will be applied for methacrylate-based resin composite restorative system. Hence, each patient will receive four restorations with different strategies. All restorative procedures will be carried out by a single operator.

After administration of local anesthetic, rubber dam will be placed. The cavity preparation was then carried out with an outline limited to caries progression. The cavities depth in mm will be measured by a periodontal probe to give an idea about the thickness of the flowable composite liner (when used) and preserve 2 mm depth for the overlying resin. Restorative systems were then be applied according to the instructions recommended by their manufactures. Sectional pre-contoured matrix with ring, and wave like contour plastic wedges was used to restore the shape of the proximal walls. Adhesive and resin composites was cured using a LED (light

emitting diode) curing unit in the standard application mode and an output of 650 mW/cm^2.

### **Clinical evaluation**

All restorations were clinically evaluated using FDI criteria. This evaluation was done at the baseline, then after 12-month and finally at 24-months.

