### **Statistical analysis:**

The Chi-Square test was used for comparison between the four groups within every follow up period, while marginal homogeneity test was used to compare the changes within each group per time.

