	4	0	0	0	0		0	0	0	0		0	0	0	0		0	0	0	0		0	0	0	0		p4=1.0	p4=1.0	p4=1.0	p4=1.0
	5	0	0	0	0		0	0	0	0		0	0	0	0		0	0	0	0		0	0	0	0					
Interproximal contact	1	30	30	30	30	p=1.0	30	30	30	30	p=1.0	30	30	30	30	p=1.0	30	30	30	30	p=1.0	29	28	27	28	p=0.784	p1=0.317	p1=0.317	p1=0.317	p1=0.317
	2	0	0	0	0		0	0	0	0		0	0	0	0		0	0	0	0		1	2	3	2		p2=0.157	p2=0.157	p2=0.157	p2=0.157
	3	0	0	0	0		0	0	0	0		0	0	0	0		0	0	0	0		0	0	0	0		p3=0.083	p3=0.083	p3=0.083	p3=0.083
	4	0	0	0	0		0	0	0	0		0	0	0	0		0	0	0	0		0	0	0	0		p4=0.157	p4=0.157	p4=0.157	p4=0.157
	5	0	0	0	0		0	0	0	0		0	0	0	0		0	0	0	0		0	0	0	0					
Postoperative (hyper-) sensitivity and tooth vitality	1	29	30	28	30	p=0.288	30	30	30	30	p=1.0	30	30	30	30	p=1.0	30	30	30	30	p=1.0	30	30	30	30	p=1.0	p1=0.317	p1=0.157	p1=0.083	p1=1.0
	2	1	0	2	0		0	0	0	0		0	0	0	0		0	0	0	0		0	0	0	0		p2=1.0	p2=1.0	p2=1.0	p2=1.0
	3	0	0	0	0		0	0	0	0		0	0	0	0		0	0	0	0		0	0	0	0		p3=0.157	p3=0.157	p3=0.157	p3=0.157
	4	0	0	0	0		0	0	0	0		0	0	0	0		0	0	0	0		0	0	0	0		p4=1.0	p4=1.0	p4=1.0	p4=1.0
	5	0	0	0	0		0	0	0	0		0	0	0	0		0	0	0	0		0	0	0	0					
Recurrent caries	1	30	30	30	30	p=1.0	30	30	30	30	p=1.0	30	30	30	30	p=1.0	30	30	30	30	p=1.0	30	30	30	30	p=1.0	p1=1.0	p1=1.0	p1=1.0	p1=1.0
	2	0	0	0	0		0	0	0	0		0	0	0	0		0	0	0	0		0	0	0	0		p2=1.0	p2=1.0	p2=1.0	p2=1.0
	3	0	0	0	0		0	0	0	0		0	0	0	0		0	0	0	0		0	0	0	0		p3=1.0	p3=1.0	p3=1.0	p3=1.0

	4	0	0	0	0		0	0	0	0		0	0	0	0		0	0	0	0		p4=1.0	p4=1.0	p4=1.0	p4=1.0
	5	0	0	0	0		0	0	0	0		0	0	0	0		0	0	0	0					
Tooth integrity (enamel cracks and tooth fractures)	1	30	30	30	30	p=1.0	30	30	30	30	p=1.0	30	30	30	30	p=1.0	30	30	30	30	p=1.0	p1=1.0	p1=1.0	p1=1.0	p1=1.0
	2	0	0	0	0		0	0	0	0		0	0	0	0		0	0	0	0		p2=1.0	p2=1.0	p2=1.0	p2=1.0
	3	0	0	0	0		0	0	0	0		0	0	0	0		0	0	0	0		p3=1.0	p3=1.0	p3=1.0	p3=1.0
	4	0	0	0	0		0	0	0	0		0	0	0	0		0	0	0	0		p4=1.0	p4=1.0	p4=1.0	p4=1.0
	5	0	0	0	0		0	0	0	0		0	0	0	0		0	0	0	0					

#USED test: Chi-Square test for comparing between groups (EXF, SDR and TNFBF) \$USED test: Marginal Homogeneity test for comparing between different follow up times as compared to baseline value

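### The stated evaluation schedule (baseline, 12 and 24 months) contradicts the results table, whose within-group p-values do not fit its own counts and headings and whose between-group test ignores the four-per-patient pairing

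*Combined protocol and SAP*

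**What the plan says.** The protocol and SAP form one document, which also carries a results table.

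- **Clinical evaluation** gives a closed list of visits: "This evaluation was done at the baseline, then after 12-month and finally at 24-months".
- **Statistical analysis** names two tests. Between groups, "The Chi-Square test was used for comparison between the four groups within every follow up period". Within groups, "marginal homogeneity test was used to compare the changes within each group per time".
- **Results, table header** has five visit blocks (baseline, 6, 12, 18 and 24 months), each with n=30 per group and its own chi-square column. The within-group columns are headed XF, XB, AFX and AFB. Each holds four values labelled p1 to p4, and the labels are not defined.
- **Results, table footnote** describes the within-group test: "Marginal Homogeneity test for comparing between different follow up times as compared to baseline value".
- **Interventions: Restorative procedures** sets the pairing: "each patient will receive four restorations with different strategies".
- **Aim of the study** looks to two years ("evaluate the effect of flowable lining resin composites on 2-year clinical performance"), as does the Introduction. **Null hypothesis** refers to "no significant difference among the four tested restorative strategies at different clinical evaluation periods". No section states a significance level or says that 24 months is the main time point.

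**The concern.** Three things in the document do not agree with each other. The table has two visits that the schedule excludes, and nothing calls them unscheduled. A reader cannot tell whether they were planned, added or printed in error.

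Some within-group p-values report change where the counts show none. Interproximal contact is 30/0 in every group through 18 months, yet values of 0.317, 0.157 and 0.083 appear in every group column.

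The between-group test is one for independent samples, although every patient contributes a restoration to each group. At stake is whether the table can be relied on as the record of what was measured and tested.

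**Working it through.** **1. Visits.** Schedule: baseline, 12, 24 months. Table: baseline, 6, 12, 18, 24 months. With nine criteria, the table implies 9 × 5 = 45 between-group tests, of which 9 × 2 = 18 are at the two extra visits. Of those 18, 16 have every restoration at score 1. The other two repeat the colour-match counts seen at every visit. Only 5 (colour match) + 1 (baseline sensitivity) + 1 (24-month contact) = 7 of 45 contain any other score. In the text available, the tooth-integrity rows and the last recurrent-caries rows show four visit blocks, not five. This is probably an extraction effect, and all entries there are score 1.

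**2. Printed between-group values.** Pearson chi-square, 2 × 4 table, 3 df, score-2 counts in the order XF, XB, AFX, AFB:

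- Colour match 2, 1, 0, 0, expected 0.75 each: 2.75/0.75 + 2.75/29.25 = 3.761, p = 0.288, as printed. Baseline sensitivity (1, 0, 2, 0) gives the same value, as printed.
- Contact at 24 months 1, 2, 3, 2, expected 2 each: 2/2 + 2/28 = 1.071, p = 0.784, as printed.

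**3. Within-group formula.** In the contact and sensitivity rows, at least one of the two visits compared is always 30/0, so the margins fix the number of changes d, all in one direction. The asymptotic statistic is d²/d = d on 1 df. Hence d = 0, 1, 2, 3 gives p = 1.0, 0.317, 0.157, 0.083. These are exactly the values that occur in the table, so this is evidently the version used.

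**4. Reading A: p1 to p4 are 6, 12, 18 and 24 months against baseline.** Values in the order XF / XB / AFX / AFB:

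| Row | Expected | Printed | Wrong |
|---|---|---|---|
| Contact p1 | 1.0 in all | 0.317 in all | 4 |
| Contact p2 | 1.0 in all | 0.157 in all | 4 |
| Contact p3 | 1.0 in all | 0.083 in all | 4 |
| Contact p4 | 0.317 / 0.157 / 0.083 / 0.157 | 0.157 in all | 2 |
| Sensitivity p1 | 0.317 / 1.0 / 0.157 / 1.0 | 0.317 / 0.157 / 0.083 / 1.0 | 2 |
| Sensitivity p2 | same | 1.0 in all | 2 |
| Sensitivity p3 | same | 0.157 in all | 3 |
| Sensitivity p4 | same | 1.0 in all | 2 |

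Total 14 + 9 = 23 of 9 × 4 × 4 = 144. The seven other criteria (112 cells) fit p = 1.0. Taking the previous visit as reference instead leaves 20 misfits.

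**5. Reading B: p1 to p4 stand for XF, XB, AFX and AFB, 24 months against baseline.** Contact changes of 1, 2, 3, 2 give 0.317, 0.157, 0.083, 0.157, which match p1 to p4. Sensitivity changes of 1, 0, 2, 0 give 0.317, 1.0, 0.157, 1.0. The value in each group's own column is right in all eight cells. Three cells misfit: sensitivity p1 under XB, AFX and AFB, where 0.317 is expected and 0.157, 0.083 and 1.0 are printed. On this reading the column headings have no function.

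**6. Pairing.** Cochran's Q = (k−1)(kΣC² − T²)/(kT − ΣR²), with k = 4, C the group counts, T their sum and R the events per patient. The table does not show R, so the range over all clusterings is given (3 df).

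- Colour match at 24 months: numerator 3 × (4×5 − 9) = 33. Events in three patients: 33/(12 − 3) = 3.667, p = 0.300. Two events in one patient: 33/(12 − 5) = 4.714, p = 0.194.
- Contact at 24 months: numerator 3 × (4×18 − 64) = 24. Events in eight patients: 24/(32 − 8) = 1.0, p = 0.801. Tightest clustering (4, 3 and 1 events in three patients, ΣR² = 26): 24/(32 − 26) = 4.0, p = 0.261.

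Within-patient permutation gives 0.50 to 0.625 and 0.75 to 0.96 respectively. The other seven criteria have no variation at 24 months.

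**The case against.** The strongest objection is that p1 to p4 are undefined, so the figure of 23 wrong cells rests on an inferred mapping. This stands. A reader might infer that 23 p-values are proven wrong. The documents do not support that, because reading B leaves every group's own value correct. The identical contact values across columns might also be one merged cell repeated when the file was read. That does not clear the table: the sensitivity p1 row differs by column, and no reading tried fits every cell. The footnote to the chi-square column also names three groups that are not this trial's, which is a further reason to check against source.

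A second objection is that nothing turns on any of this, since no printed p-value is near 0.05. That also stands as to consequence, but it does not make contradictory text correct.

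A reader might also infer a serious multiplicity problem: 45 independent tests at 0.05 would give 1 − 0.95^45 = 0.90. That figure does not apply, because 38 of the 45 tests have no variation and the smallest between-group p is 0.288. The absent alpha and undesignated time point are gaps in wording, and the two-year aim already points to 24 months. Nor do the documents show that the 6- and 18-month visits were invented or added to gain significance. They show only a mismatch.

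**Conclusion.** The point holds in this form. The visit contradiction is plain in the text and needs no assumption. The within-group p-values for two criteria do not fit the counts and headings: 23 of 144 cells on the visit reading, three on the group reading. Both counts assume the asymptotic marginal homogeneity test and a faithfully extracted table. The independent-samples chi-square does not match the four-per-patient design.

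The effect on inference is nil at an assumed alpha of 0.05. The within-group minimum is 0.083 before and after correction. At 24 months no clustering of events within patients could bring the matched p-value below 0.194 (Cochran's Q). These are errors that should be corrected for the record. They do not show a false or missed finding.

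**What to change.** 1. Reconcile the Clinical evaluation section and the results table on which visits took place. Label any visit outside the schedule as unscheduled.
2. Define p1 to p4. Then recompute the within-group p-values for contact and sensitivity from the counts, and print each under its own group and visit.
3. Replace the between-group chi-square with a matched four-group test, either Cochran's Q or a within-patient permutation. At 24 months only colour match and contact need recomputing.
4. Add one line stating the alpha and that 24 months is the main time point, marked as a clarification made after the data were seen. No adjustment over the nine criteria is asked for.

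The cost is wording plus a small recomputation from existing patient-level data: two between-group tests at 24 months and, on the visit reading, 23 within-group cells. The matched test addresses the four-group null only. It does not by itself separate the liner effect from the matrix effect.
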